6.0 Local Number of Subjects

6.1 *Indicate the total number of subjects who will be enrolled or records that will be reviewed through Upstate.*

Based on the power analysis and overage for dropouts a maximum of 33 subjects will be enrolled in the study. The goal is to have at least 20 subjects complete all testing.

6.2 *If applicable, indicate your screen failure rate, i.e., how many subjects you expect to screen to reach your target sample.*

We are attempting to keep the inclusion/exclusion criterion broad and we are including patients with upper and lower extremity symptoms. After phase one of this project, we will have a better idea of the screening failure rate. Given the lack of alternative treatments for this condition and the impact symptoms can have on quality of life, we feel that potential subjects will be highly motivated to be involved in the study.

6.3 Justify the feasibility of recruiting the proposed number of eligible subjects within the anticipated recruitment period. For example, how many potential subjects do you have access to? What percentage of those potential subjects do you need to recruit?

Recruitment for this study may be challenging due to the rarity of the condition. We are partnered with the Upstate PM&R department who routinely see patients with this condition. We will also send recruitment materials to pain management specialists and surgeons inside and outside the Upstate system.

7.0 Inclusion and Exclusion Criteria

7.1 Describe, in bullet points, the criteria that define who will be included in this study:

Eligible subjects will meet all of the following criteria:

- 1) 18 years or older
- 2) Upper or lower extremity CRPS Type 1 (also called RSD-Reflex Sympathetic Dystrophy) of at least 6 months. It is anticipated that most potential subjects will have an established diagnosis of CRPS by a healthcare provider. Study members will confirm the diagnosis by using the Budapest Criteria, which is the most current diagnostic criterion for CRPS.
 - a. Budapest Criteria- To be diagnosed with CRPS individuals must have continued pain, which is disproportionate to inciting event, no other diagnosis that better explains the symptoms and 1 symptom in 3 of the 4 categories and 1 sign in 2 of the 4 categories below.
 - i. Sensor-hyperalgesia and/or allodynia
 - ii. Vasomotor-temperature asymmetry, skin color changes or asymmetry
 - iii. Sudomotor/Edema-Edema and/or sweating changes and/or sweating asymmetry
 - iv. Motor/trophic-reduced ROM, weakness, tremor, dystonia, or changes in hair, nail, or skin.
- 3) Pain rating on NPRS of at least 4/10
- 4) No initiation of a new intervention (i.e., medication, rehab, injections) in the previous 2 months.

- 5) No plan to initiate a new intervention during the study treatment timeframe (4 weeks).

7.2 Describe, in bullet points, the criteria that define who will be excluded from this study:

Potential subjects with any of the following will be excluded.

- 1) A history of seizures or epilepsy
- 2) Intracranial metallic devices
- 3) Pacemaker
- 4) Intrathecal infusion pumps
- 5) Brain or spinal cord stimulators with epidural electrodes
- 6) Other ferromagnetic metallic intracranial implants
- 7) Apparent mental or psychiatric disorder that prevents adequate informed consent
- 8) Current pregnancy
- 9) Non-English speaking

7.3 Indicate whether you are specifically recruiting or targeting any of the following special populations in your study using the checkboxes below.

N/A

- Adults unable to consent (*complete and upload Supplemental Form A*)
- Minors (under 18 years old)
- Pregnant women
- Prisoners

6.4 Indicate if you will include minorities (American Indians, Alaskan Native, Asian, Native Hawaiian, Pacific Islander, Black [not of Hispanic origin] and Hispanic) as Federal mandates require that you include minorities unless you can justify their exclusion

- Yes
- No, Justify:

8.0 Vulnerable Populations

8.1 For research that involves pregnant women, review, complete and upload Supplemental Form B: Research Involving Pregnant Women, Fetuses, or Neonates.

- Confirmed
- N/A: This research does not involve pregnant women.

8.2 *For research that involves neonates of uncertain viability or non-viable neonates, review, complete and upload Supplemental Form B: Research involving Pregnant Women, Fetuses, or Neonates.*

Confirmed

N/A: This research does not involve non-viable neonates or neonates of uncertain viability.

8.3 *For research that involves prisoners, review, complete and upload Supplemental Form C: Research involving Prisoners*

Confirmed

N/A: This research does not involve prisoners.

8.4 *For research that involves minors (under 18 years), review, complete and upload Supplemental Form D: Research involving Minors*

Confirmed

N/A: This research does not involve minors (under 18 years),

8.5 *Consider if other specifically targeted populations such as students, employees of or educationally or economically disadvantaged persons are vulnerable. Provide information regarding their safeguards and protections, including safeguards to eliminate coercion or undue influence.*

N/A

9.0 Eligibility Screening

9.1 *Describe screening procedures for determining subjects' eligibility. Screening refers to determining if prospective participants meet inclusion and exclusion criteria. Include (upload) all relevant screening documents with your submission (e.g. screening protocol, script, questionnaires).*

Potential subjects will be screened via phone using a standardized screening document and a TMS screening questionnaire. If they meet the eligibility criterion they will be invited to participate in the study. Additional screening to confirm the diagnosis of CRPS using the Budapest criterion will be performed at the first session. On their arrival, participants will complete the same TMS questionnaire again (about 10 minute) to ensure their medical status has not changed.

N/A: There is no screening as part of this protocol.

10.0 Recruitment Methods

- N/A: Subjects will not be recruited.

10.1 Describe source of subjects: When, where, and how potential subjects will be recruited.

NOTE: Recruitment refers to how you are identifying potential participants and introducing them to the study; for example, physician referral, database search, reviewing medical records, research participant groups/help/advocacy groups, advertising companies, call centers, in person announcements / presentations, etc.

The primary recruitment method will be through physician or other healthcare provider referral. Recruitment materials will be left with medical offices and placed in waiting rooms, when approved. Flyers, media advertisement, social media, and word of mouth will also be utilized.

10.2 Describe how you will protect the privacy interests of prospective subjects during the recruitment process.

NOTE: Privacy refers to an individual's right to control access to him or herself. This is NOT asking about confidentiality of data.

The recruitment screening process will occur via phone. If the potential subject is not comfortable with a phone screening, they will be offered a private meeting. Subjects will be allowed to ask questions about the study protocol during the screening or at another time. Screening will be performed by IRB-approved study personnel, who are aware of privacy standards.

10.3 Identify all materials that will be used to recruit subjects and upload copies of these documents (such as telephone scripts, flyers, questionnaires, posters, letters, e-mails, pamphlets, advertisements).

A flyer, telephone script, tear-off pad flyer, and language to be used in a social media post were uploaded.

11.0 Research Methods & Procedures

Provide a detailed description of the methods and procedures that will be used to carry out the study. Include a summary of study visits and procedures (i.e., schedule of events table) in the space below or as an attachment.

Please make sure to include:

- Dosing of drugs and other details of study drug administration and study treatments
- A list and description of any experimental procedures
- A list and description all tests & procedures that would not be done if the subjects were not in the study
- An explanation how study participation differs from the standard of care
- Procedures being performed to monitor subjects for safety or to minimize risks

Interventions: 4 weeks

- Treatment will start (week 1) with 4 consecutive rTMS and 2 PT sessions (skipping weekends)
- Sessions will continue at 2 times a week for a total of 10 sessions
- Measurements will occur at:
 - The first visit (except GROC)
 - The last visit of each week
 - At 4 time points after the termination of the interventions-via e-mail survey
 - 4 weeks
 - 3 months
 - 6 months
 - 1 year

First Session:

- Screening (Budapest Criterion, and TMS screening)
- Informed consent- during the phone screening subjects will be given the opportunity to have informed consent documents sent to them via email. Subjects will be given time to read the documents and ask questions about the study before agreeing to participate.
- Randomization
- Baseline measurements
- rTMS/sham rTMS session
- PT session

Subsequent Sessions (9):

- TMS screening
- rTMS/sham rTMS (the first week 2/4 sessions will not include a PT session)
- PT session
- Repeat measurements will be taken at the end of each week (4 in total)

Test and measures: All outcome measures are self-reported and collected using REDCap.

- Primary
 - Numeric Pain Rating Scale (NPRS) (0-10): Average score for the week

- Secondary Measures

- Numeric Pain Rating Score (0-10): Worse and least pain intensity over past 24 hours
- NIH Patient-Reported Outcomes Measurement Information System (PROMIS): Pain interference, pain behavior, physical functioning, satisfaction with discretionary social activity, satisfaction with social roles, fatigue, depression, anxiety, and anger.
- Patient Global Impression of Change (GROC) (only measured at follow-up)- scale rated from 0 (not important) to 7 (a very great deal important).
- Patient Global Impression of Change Impact (GROCI) (only measured at follow-up)- scale rated from 0 (not important) to 7 (a very great deal important).
- Patient Acceptable Symptom State (PASS): “Considering all the different ways your pain symptoms are affecting you, if you were to stay in this state for the next few months, do you consider that your current state is satisfactory?” (Yes/No)
- Grip Strength (Subjects with UE symptoms only)- Measured using a dynamometer bilaterally.
- Leg Press 1 Repetition Maximum Test (Subjects with LE symptoms only): The subject will perform 2 warm-up sets with light resistance. Weight will be increased with the goal of finding the 1 repetition maximum weight within 4 trials. A 2-minute rest period will be given between trials.
- Patient Specific Functional Scale: Goals are set by PT and subject. The patient rates their ability to complete the task described in to goal on a 0(unable to perform) to 10 (Able to perform activity at the same level as before injury or problem).
- Adverse events
- Participant disposition: Who was enrolled/reasons for exclusion, reason for dropout (if known)

Interventions:

- rTMS:

- rTMS will be delivered using a commercially available magnetic stimulator (Rapid², Magstim Inc., Eden Prairie, MN) with a figure-of-8 coil at 10 Hz. With subjects in a seated position, the coil will be positioned on the scalp, contralateral to the subject’s symptomatic side. Coil orientation will be optimized for stimulation of the abductor pollicis brevis.
- Targeting:

Subjects will wear a lycra cap so marks can be made to facilitate proper targeting. Single-pulse stimulations will be delivered over various locations of the contralateral primary motor cortex to identify the optimal location for stimulation of the target muscle. Motor evoked potentials (MEP) of the abductor pollicis brevis will be monitored using electromyography (EMG) (Motion Lab Systems Inc., Baton Rouge, LA). Once the optimal stimulation position is identified a mark will be made on the lycra cap. The motor threshold (MT) of the muscle will then be

identified by systematically adjusting the pulse intensity. The MT will be considered the lowest stimulation intensity at which 5 out of 10 MEPs have a peak-to-peak amplitude of at least 50 microvolts, measured using RMG of the abductor pollicis brevis.

○ Parameters:

rTMS will be performed at the identified optimal location at 10Hz using an intensity that is 80% of the MT. Pulse trains will be delivered for 10 seconds, with a 30 second rest for 20 repetitions. This will result in a total of 2,000 pulses of magnetic stimulation.

○ Safety:

The most common side effects during stimulation are local discomfort and headaches. Subjects will be asked to inform the researcher if they are unable to tolerate the rTMS. If they cannot tolerate the stimulation the subjects will be given two options. The first option will be to reduce the stimulation intensity to a point that is tolerable. The second option will be to stop the stimulation. If they elect to stop the stimulation the subject can decide to end participation in the study or try another session at a subsequent date. Subjects will also be monitored for EMG activity at the abductor pollicis brevis and visual twitch response at other muscles. If this activity increases over the course of the stimulation the intensity will be reduced.

- Sham rTMS:

- Sham rTMS will be performed using the same coil and delivery device used in the real rTMS group. The sham group will start with the same localization procedure as the real rTMS group. The magnet will then be moved over the vertex of the skull and the intensity will be dropped to 5% of the maximal stimulation output or half of the treatment intensity (40% of MT) used in the real rTMS group, whichever is lower. Subjects in both groups will be told that after localization, the stimulation intensity will be lowered for the treatment. The sham group will be told that with this lower intensity they may experience minimal to no sensation from the stimulus. Allocation will be disclosed to all participants after the last data collection timepoint.

- Rehabilitation:

- Rehabilitation will consist of education, value-based goal setting, Graded Motor Imagery (GMI) (3 components described below), meditation, and graded activity. Subjects will complete activities at treatment sessions and be asked to perform certain treatment activities at home.

- Week 1: Pain education, functional value-based goal setting, laterality training (first component of GMI), one task for graded activity (task-based on patient goals)
 - Week 2: Continue week 1 activity, add graded motor imagery (second component of GMI), progress 1st graded activity, and initiate 2nd graded activity exercise.
 - Week 3- Mirror therapy (third component of GMI), add meditation, assess knowledge and update education as needed, progress graded activity 1 and 2, and add 3rd graded activity if appropriate based on patient goals.
 - Week 4- Continue with week 3 activities. Discuss experience with meditation and progress graded activity as tolerated.
- Pilot Testing
- This is a new treatment protocol for our lab. To test and adjust the logistics of the protocol 1-3 subjects will be enrolled as pilot subjects. The subjects will complete the standard protocol but will not be randomized. All 1-3 subjects in the pilot testing will receive the real rTMS.

11.1 Describe what data, including long-term follow-up, will be collected.

NOTE: For studies with multiple data collection points or long-term follow up, consider including a schedule or table in your response.

Measurements:

- The first visit
 - All instruments except the GROC
 - Basic demographics and other relevant medical information will be collected at this visit
- The last visit of each week
 - All outcome instruments will be collected
- All outcome instruments will be collected at 4-time points after the termination of the interventions-via REDCap e-mail survey or mailed survey if the subject does not have access to e-mail.
 - 4 weeks
 - 3 months
 - 6 months
 - 1 year

List, and upload, any instruments or measurement tools used to collect data (e.g. survey, scripts, questionnaire, interview guide, validated instrument, data collection form).

All of the listed instruments will be uploaded with this IRB submission.

- Numeric Pain Rating Score (0-10): Weekly average and worst and least pain intensity over past 24 hours
- NIH Patient-Reported Outcomes Measurement Information System (PROMIS): Pain interference, pain behavior, physical functioning, satisfaction with discretionary social activity, satisfaction with social roles, fatigue, depression, anxiety, and anger.
- CRPS Severity Score
- Patient Global Impression of Change (GROC) (only measured at follow-up)- scale rated from -7 (a very great deal worse) to +7 (a very great deal better) with 0 being about the same.
- Patient Acceptable Symptom State (PASS): Considering all the different ways your pain symptoms are affecting you, if you were to stay in this state for the next few months, do you consider that your current state is satisfactory?" (Yes/No)
- Adverse events
- Participant disposition: Who was enrolled/reasons for exclusion, reason for dropout (if known)

11.2 Describe any source records that will be used to collect data about subjects (e.g. school records, electronic medical records).

No records will be used. All data will be collected directly from the patient.

11.3 Describe whether individual subject results (such as results of investigational diagnostic tests, genetic tests, or incidental findings) will be shared with subjects or others (e.g., the subject's primary care physicians) and if so, describe how it will be shared.

Data will not be shared with subjects.

11.4 Indicate whether or not generalized study results will be shared with subjects or others, and if so, describe how these will be shared.

Results will not be shared with subjects unless requested.

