5.0 Data Management and Analysis

5.1 Describe the data analysis plan, including any statistical procedures. This section applies to both quantitative and qualitative analysis

- 1) Primary: NPRS weekly average: 2-way ANOVA for within and between effects.

Secondary:

- 2) NPRS worse/least 24 hours: 2-way ANOVA for within and between effects.
- 3) NPRS number reaching 30% improvement: Descriptive (%), Logistic Regression
- 4) PROMIS: 2-way ANOVA for within and between effects.
 - a. Pain interference
 - b. Pain behavior
 - c. Physical functioning

- d. Satisfaction with discretionary social activity
 - e. Satisfaction with social roles
 - f. Fatigue
 - g. Depression
 - h. Anxiety
 - i. Anger
- 5) GROC: 2-way ANOVA for within and between effects.
 - 6) GROCi: 2-way ANOVA for within and between effects.
 - 7) PASS: Logistic Regression
 - 8) Grip Strength: 2-way ANOVA for within and between effects.
 - 9) 1 Repetition Max Leg Press: 2-way ANOVA for within and between effects.

5.2 *If applicable, provide a power analysis for the number of subjects to be included. If qualitative research, so state, and provide general justification for the total number of subjects proposed.*

NOTE: This may not apply to certain types of studies, including chart/records reviews, survey studies, or observational studies. This question is asked to elicit whether the investigator has an adequate sample size to achieve the study objectives and justify a conclusion.

The pain numeric rating scale (NPRS) MCID ranges from 1 to 2.5 in the literature. Salaffi et al (2003) found that a reduction of 2.0 points was associated with a rating of “much better” for patients with chronic pain. A review of the literature looking at pain ratings for patients with CRPS showed standard deviations approximately 1.0 to 2.0. Effect size was calculated using a 2-point NPRS change and a standard deviation of 1.7. G*Power 3.1.9.7 was used to calculate the sample size based on a repeated measures ANOVA with between and within measures comparisons. A partial η^2 of .07 (moderate effect size) gave an effect size of .274, $\alpha=0.05$, and power was set at 80%. Sample size was calculated for 2 groups, 4 measurements, with a correlation of .5, and nonsphericity of 1. This resulted in a group size of 10 participants for a total of 20 subjects. To account for dropouts up to 36 subjects will be enrolled in this study.

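### GROC is defined as a 0 to 7 importance rating in section 11.0 but as a -7 to +7 change rating in section 11.1, and the 11.0 scale records no direction of change

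*Combined protocol and SAP*

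**What the plan says.** Section 11.0, under secondary measures, defines the item as "Patient Global Impression of Change (GROC) (only measured at follow-up)- scale rated from 0 (not important) to 7 (a very great deal important". The entry directly after it reads "Patient Global Impression of Change Impact (GROCI) (only measured at follow-up)- scale rated from 0 (not important) to 7 (a very great deal important". Apart from the item name, the two descriptions are the same.

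Section 11.1, in its list of data-collection instruments, gives GROC again under the same name and acronym, but with a "scale rated from -7 (a very great deal worse) to +7 (a very great deal better) with 0 being about the same". GROCI does not appear in that list.

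Section 5.1 plans separate analyses for the two items among the secondary outcomes: "GROC: 2-way ANOVA for within and between effects" and "GROCi: 2-way ANOVA for within and between effects". It gives no range or scoring direction for either.

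Section 11.1 also says: "All of the listed instruments will be uploaded with this IRB submission". Those forms are not part of the protocol text.

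**The concern.** GROC is meant to capture the patient's own view of whether they have changed, and in which direction. The 11.0 anchors ask instead how important something is. A patient with an important deterioration and a patient with an important improvement could both answer 7.

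The hypothesis in section 1.2 is that real rTMS plus rehabilitation gives better outcomes than sham plus rehabilitation. A score without direction cannot speak to better or worse, however it is analysed. Whoever builds or checks the REDCap form from section 11.0 would be following the protocol and would still collect ratings that cannot serve this purpose.

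**Working it through.** There is no stated figure to reproduce, and the point does not depend on alpha, power, effect size or N. The check is a comparison of the texts.

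**Side by side**

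| | GROC in 11.0 | GROC in 11.1 | GROCI in 11.0 |
|---|---|---|---|
| Range | 0 to 7 | -7 to +7 | 0 to 7 |
| Integer points | 7 - 0 + 1 = 8 | 7 - (-7) + 1 = 15 | 7 - 0 + 1 = 8 |
| What is rated | importance | direction and size of change | importance |
| Meaning of 0 | not important | about the same | not important |
| Meaning of 7 | highest importance | greatest improvement | highest importance |

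**Can one scale be recoded into the other?** No. The shared values 0 and 7 have different meanings, and the quantity being rated differs. An 11.0 score of 7 is compatible with +7 or with -7 on the 11.1 scale.

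**Can direction be recovered from another GROC rating?** No. Sections 11.0 and 11.1 both leave GROC out of the first visit, so there is no baseline GROC value to compare with. Direction has to come from the response itself.

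**Is one definition superseded?** Nothing indicates this. Both stand in current text. The list of version 2 changes in section 4.1 does not mention GROC.

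**Does the analysis plan settle it?** Not explicitly. Section 5.1 names the method and no range. It does treat GROC and GROCi as two outcomes, which fits 11.1 better, because under 11.0 their printed scales are identical.

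**When is the first rating?** Both sections say that GROC is measured only at follow-up. Section 11.1 also says that all outcome instruments are collected at the last visit of each treatment week, and then at 4 weeks, 3 months, 6 months and 1 year after treatment. On that reading the first GROC rating falls at the end of week 1. If follow-up means only the post-treatment surveys, it falls 4 weeks after treatment ends. A form check should allow for the earlier date.

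**What else depends on GROC?** The primary outcome is the weekly average NPRS, and the sample size in section 5.2 is built on the NPRS. Neither uses GROC.

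**The case against.** The strongest reply is that the slip may exist only on paper. Section 11.1 lists the instruments actually used for data collection, gives the coherent two-sided scale, and says that the forms go to the IRB. The item's name refers to change, and the 11.0 anchors match the next entry so closely that a copying error is the natural explanation, although that is an inference. The fielded form may well be right. This stands: the documents do not show that the wrong scale was used, and any loss of data is conditional. It does not remove the contradiction in the definition of a listed outcome.

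Three stronger readings are tempting, and the documents do not support them.

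- A reader might infer that 11.0 merely cuts off the lower half of the 11.1 scale, losing the 7 negative levels out of 15 and keeping the improvement side. The 11.0 anchors rate importance, so improvement is not recorded either. A count of lost levels misdescribes the problem.
- A reader might infer that under 11.0 GROC and GROCI become the same question. Neither section prints the question wording. Only the scale descriptions are shown to be identical.
- A reader might treat GROC as the trial's main measure of global improvement. Section 5.1 lists it as one secondary outcome among several, with no special status. The NPRS outcomes, including the 30% responder outcome, and the PROMIS domains also bear on change, and PASS is another overall rating. They limit the damage, although none replaces the patient's own rating of change.

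It is also fair to say that the two instrument lists differ more widely. Section 11.1 omits grip strength, leg press and the Patient Specific Functional Scale, and includes a CRPS Severity Score that 11.0 lacks. Those differences are worth clearing up in the same edit but are separate from this point.

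**Conclusion.** The concern holds as an internal inconsistency in the definition of a secondary outcome. It should not be read as a deliberate design choice. Sections 11.0 and 11.1 define GROC with different ranges, anchors and constructs, and the 11.0 version cannot show whether a patient improved or worsened. That much rests on the printed text alone and is certain.

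The consequence for the data rests on one assumption that cannot be checked here: that the REDCap form follows 11.0. If it does, the GROC ANOVA cannot address benefit, and the missing direction cannot be recovered from the ratings. If the form follows 11.1, only the protocol text is wrong. In either case the effect is confined to GROC. The correction should be made because it is cheap and because ratings taken on the wrong scale could not be repaired.

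**What to change.** 1. In section 11.0, replace the GROC anchors with the protocol's own section 11.1 definition.
2. Keep the 0 to 7 importance scale for GROCI only, and add GROCI to the instrument list in section 11.1.
3. In section 5.1, state that GROC is analysed on the -7 to +7 scale, with positive values meaning better.
4. Check that the REDCap form matches before the first GROC rating, taking the end of week 1 as the earliest date. If any ratings already exist, record which scale they used.

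The cost is a few lines of text in three sections and one form check. No procedure, visit or sample size changes.

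### GROCI is an unsigned importance rating analysed without the direction of change, and the GROC scale that should supply that direction is defined in two conflicting ways

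*Combined protocol and SAP*

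**What the plan says.** Section 11.0 (secondary measures) describes the impact item as "Patient Global Impression of Change Impact (GROCI) (only measured at follow-up)- scale rated from 0 (not important) to 7 (a very great deal important"). Section 5.1 gives its analysis as "GROCi: 2-way ANOVA for within and between effects", and for the companion item "GROC: 2-way ANOVA for within and between effects". No section ties the GROCI score to the direction of the GROC rating.

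GROC has two definitions. Section 11.0 has "Patient Global Impression of Change (GROC) (only measured at follow-up)- scale rated from 0 (not important) to 7 (a very great deal important"), which are the anchors used for GROCI. The instrument list in section 11.1 has "scale rated from -7 (a very great deal worse) to +7 (a very great deal better) with 0 being about the same".

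On timing, section 11.0 marks both items as follow-up measures only. The first-visit rule in section 11.1, however, reads "All instruments except the GROC" and does not name GROCI, and GROCI is absent from the instrument list in the same section. After baseline there are four weekly ratings ("Repeat measurements will be taken at the end of each week (4 in total")) and four later ones ("All outcome instruments will be collected at 4-time points after the termination of the interventions").

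**The concern.** An importance rating says how much a change mattered, not which way it went. Averaged by arm, it adds important improvements to important deteriorations. Worsening is foreseeable: section 17.1 expects temporary exacerbation of symptoms in some subjects during rehabilitation, and the GROC scale in section 11.1 has a worse side. If the arms differ in the balance of better and worse, the GROCI comparison can miss the difference or favour the wrong arm.

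The conflict over the GROC scale makes this harder to repair. If GROC is collected on the section 11.0 anchors, it has the same defect, and no GROC rating would supply a sign for GROCI.

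A smaller matter is interpretation. Section 5.1 gives GROC and GROCI the same ANOVA wording as NPRS. NPRS has a baseline value, so its time effect includes change from baseline. GROC and GROCI are ratings of change with no meaningful baseline, and section 5.1 does not say which ANOVA effect is the treatment effect for them.

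**Working it through.** **The plan's own figure.** The documents give no power or sample size for GROC or GROCI. The one calculation, in section 5.2, concerns NPRS. With f = sqrt(0.07/0.93) = 0.274, 2 groups, 4 measurements, correlation 0.5, nonsphericity 1 and alpha 0.05, the noncentrality is f² × N × 4/(1 - 0.5). At N = 20 the within effect and the within-by-between interaction each have power 0.811, so the stated 20 reproduces. Nothing below changes it.

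**Illustration of a null result.** Assumed values: 10 per arm, importance 5 for anyone who changed and 0 for anyone who did not.

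| Arm | Better | Worse | Same | Unsigned mean | Signed mean |
|---|---|---|---|---|---|
| A | 7 | 2 | 1 | (7 + 2) × 5/10 = 4.5 | (35 - 10)/10 = +2.5 |
| B | 3 | 6 | 1 | (3 + 6) × 5/10 = 4.5 | (15 - 30)/10 = -1.5 |

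The unsigned difference is 4.5 - 4.5 = 0. The signed difference is 2.5 - (-1.5) = 4.0.

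**Illustration of a reversal.** Same assumptions.

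| Arm | Better | Worse | Same | Unsigned mean | Signed mean |
|---|---|---|---|---|---|
| A | 6 | 0 | 4 | 30/10 = 3.0 | +30/10 = +3.0 |
| B | 2 | 7 | 1 | (2 + 7) × 5/10 = 4.5 | (10 - 35)/10 = -2.5 |

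Arm B scores higher on the unsigned mean although most of its subjects worsened.

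**How often this would matter.** A mixed ANOVA was simulated with 10 per arm, 4 or 8 post-baseline times, correlation 0.5, SD 1.5, 2.0 or 3.0, scores rounded and limited to -7 to +7, and 3,000 runs per setting. The absolute value of the signed score stood in for the unsigned rating. The means and SDs are assumptions, because the documents give none. The table shows how often the between-arm test rejects at 0.05.

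| Arm means | Signed score | Unsigned score |
|---|---|---|
| +m and -m, m = 2, 3 or 4 | 95% to 100% | 4% to 6% |
| +3 and 0 | 77% to 100% | 34% to more than 99% |

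With opposite changes of equal size, the unsigned score rejects at about the nominal alpha. With improvement in one arm only, it loses power in most settings but is not blind. All simulated times were post-baseline, so the loss comes from the missing sign alone.

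**What the time effect can show.** Suppose GROC is +4 at every post-baseline visit in one arm and 0 at every visit in the other.
- Time effect: the visit means do not change, so it is 0.
- Interaction: the arm difference is 4 - 0 = 4 at every visit, so it is 0.
- Between-arm effect: 4 - 0 = 4.

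Only the between-arm effect carries the treatment comparison.

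**The case against.** Several points on the other side are sound.

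- A reader might infer that the missing baseline is what hides opposite changes. It is not. A baseline score on a rating of change would have no meaning, and the simulation shows the masking arising without one.
- A reader might infer that GROC is masked as well. On the signed scale in section 11.1, opposite directions appear directly in the between-arm effect. GROC shares the defect only under the section 11.0 anchors.
- A reader might infer that the planned ANOVA will report no change despite sustained benefit. Section 5.1 plans between as well as within effects, and the hypothesis in section 1.2 compares real with sham rTMS. A flat time effect correctly says that ratings did not drift. It misleads only if read as change from baseline, and the plan does not say that it will be.
- Full masking needs opposite changes of similar size. Section 20.1 says that sham subjects, who also receive rehabilitation, could improve, so the illustrations are deliberately adverse.
- The full GROCI item wording is not in the documents, only its anchors. If the form confined the rating to improvements, the problem would shrink.

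These limit the size and reach of the point. They do not supply the missing rule: the plan analyses GROCI by itself, and no section says how direction enters.

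**Conclusion.** The point holds for GROCI as the plan is written. An unsigned importance score analysed alone cannot separate benefit from harm, and its between-arm result can be diluted, null or reversed when some subjects worsen. The illustrated size is a signed difference of 4.0 points against an unsigned difference of 0. That rests on assumed counts and a uniform importance of 5, and on reading the anchors as applying to change in either direction.

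The two GROC definitions contradict each other and must be reconciled, because the repair for GROCI depends on a signed GROC. The documents do not support the wider claim that every benefit would be hidden, or that the absence of a baseline is itself a fault. For the time effect, what is missing is a statement of how it is to be read.

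The consequence is limited: both outcomes are secondary, and the NPRS analysis and its sample size are untouched.

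**What to change.** 1. In section 11.0, replace the GROC anchors so that the signed -7 to +7 scale of section 11.1 is the one collected, and check that the REDCap form matches. Add GROCI to the section 11.1 instrument list. State in both sections that GROCI, like GROC, is omitted at the first visit.
2. In section 5.1, analyse GROCI multiplied by the sign of GROC at the same visit (+1, 0 or -1).
3. In section 5.1, for GROC and signed GROCI, name the between-arm difference over the post-baseline visits as the treatment effect and list those visits. State that the time effect describes drift across post-baseline ratings, not change from baseline. Label any within-arm comparison of the mean with 0 as descriptive, since it does not address real against sham.

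The cost is a few lines of text. No new item is needed provided GROC is collected on the signed scale; ratings taken on the 0 to 7 anchors would supply no sign. One small drawback is that signed GROCI is missing whenever GROC is not completed at the same visit.
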